10.4 Participant Characteristics

Demographic characteristics will be summarized using descriptive statistics.

10.5 Analysis of Primary Objective

The sensitivity and specificity will be summarized along with 95% CI using the simple asymptotic method with continuity correction. PPV and NPV will also be summarized along with 95% CI using the simple asymptotic method with continuity correction.

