10.3 Sample Size

The sample size justification of the pilot study is based on the primary objective of estimating the sensitivity and specificity for PSMA-PET for detecting extra-prostatic extension of cancer at the nerve bundles. The sensitivity and specificity will be calculated using both the left and right nerve bundles, based on the gold standard of whole-mount pathology. A sample size of 50 patients would therefore generate 100 data points. Assuming about 20% of the 100 left and right nerve bundles are not evaluable. Then we could have at least 80 data points.

Based on the preliminary data, the prevalence of extra-prostatic extension is about 35%. The sensitivity of PSMA-PET is anticipated to be 90%. A sample size of 80 would provide a two-sided 95% sensitivity confidence interval with a width of at most 0.23. The specificity of PSMA-PET is anticipated to be 76%. A sample size of 80 would provide a two-sided 95% specificity confidence interval with a width of at most 0.25. All calculations will be based on the simple asymptotic method with continuity correction.

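### The continuity-corrected Wald interval puts the lower limit for sensitivity (and NPV) too high when PET misses few bundles, and the planned width of 0.23 depends on an unstated cut at 1.00

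*Combined protocol and SAP*

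**What the plan says.** Section 10.5 fixes the interval for the primary result: "The sensitivity and specificity will be summarized along with 95% CI using the simple asymptotic method with continuity correction". The predictive values are treated the same way: "PPV and NPV will also be summarized along with 95% CI using the simple asymptotic method with continuity correction". Section 10.3 uses the same method for planning: "All calculations will be based on the simple asymptotic method with continuity correction".

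The planning values in Section 10.3 are: "Based on the preliminary data, the prevalence of extra-prostatic extension is about 35%. The sensitivity of PSMA-PET is anticipated to be 90" per cent; and "The specificity of PSMA-PET is anticipated to be 76" per cent. The precision claims are "A sample size of 80 would provide a two-sided 95% sensitivity confidence interval with a width of at most 0.23" and "A sample size of 80 would provide a two-sided 95% specificity confidence interval with a width of at most 0.25". The unit of analysis is the bundle: "The sensitivity and specificity will be calculated using both the left and right nerve bundles".

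Neither section says what happens when a limit falls outside 0 to 1. Neither names a score or exact interval, or a fallback for few or no misses.

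**The concern.** The Wald interval takes its width from the estimated proportion. As the estimate approaches 1 the estimated standard error shrinks to zero, the upper limit passes 1, and the lower limit moves up too close to the estimate. The continuity correction adds only 1/(2n) on each side.

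The plan expects sensitivity of 90% on about 28 positive bundles, and the preliminary data in Section 3.1 gave 24/26 (92%). Results close to 1 are therefore likely. Sensitivity with its interval is half of the primary endpoint, and the error flatters the test: a lower limit that is too high understates how often extension at a nerve bundle might be missed.

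**Working it through.** **Inputs.** From Section 10.3: 80 evaluable bundles, prevalence 35%, sensitivity 0.90, specificity 0.76, two-sided 95% (z = 1.96). So 80 × 0.35 = 28 positive and 52 negative bundles. From Section 3.1: preliminary sensitivity 24/26. Bundles are treated as independent throughout.

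**1. The plan's own widths.** The planned interval is p ± [z√(p(1−p)/n) + 1/(2n)].

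- Sensitivity: 1.96 × √(0.90 × 0.10/28) = 0.1111; 1/56 = 0.0179; half-width 0.1290. The interval is 0.771 to 1.029, width 0.258. Cut at 1.00, the width is 1 − 0.771 = 0.229.
- Specificity: 1.96 × √(0.76 × 0.24/52) = 0.1161; 1/104 = 0.0096; half-width 0.1257. The interval is 0.634 to 0.886, width 0.251, and no cut is needed.

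The corrected and cut version reproduces both printed figures (0.23 and 0.25). The uncorrected version gives 0.222 and 0.232. The authors therefore appear to have cut at 1.00 without recording it. Uncut, the upper limit exceeds 1 for every result of 24/28 or better, which is 86% of trials at 0.90.

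**2. Lower limits with 0 to 2 misses.** The tail area is P(X ≥ x) for n = 28, with the true sensitivity set at the lower limit. For a 95% interval it should be about 2.5%.

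| Result | Planned, cut at 1 | Tail area | Wilson | Tail area |
|---|---|---|---|---|
| 26/28 | 0.815–1.000 | 8.8% | 0.774–0.980 | 3.1% |
| 27/28 | 0.878–1.000 | 12.7% | 0.823–0.994 | 3.0% |
| 28/28 | 0.982–1.000 | 60.4% | 0.879–1.000 | 2.7% |

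At 28/28 the standard error is zero, so the planned limit is just 1 − 1/56 = 0.982, and (55/56)^28 = 0.604. The Wilson limit there is 28/(28 + 1.96²) = 0.879. The exact limit is 0.025^(1/28) = 0.877. The cut planned interval is 0.018 wide, against 0.123 for the exact interval.

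**3. How often this arises.** P(X ≥ 26 of 28) is 46% at 0.90 and 63% at 24/26. P(28/28) at 0.90 is 0.90^28 = 5.2%.

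**4. Coverage for sensitivity (exact binomial enumeration).**

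| Setting | Planned | Wilson |
|---|---|---|
| n = 28, true 0.87 | 88.8% | 95.7% |
| n = 28, true 0.88 | 96.8% | 95.7% |
| n = 28, true 0.90 | 94.3% | 94.5% |
| n = 28, true 24/26 | 89.3% | 94.0% |
| Positives ~ Binomial(80, 0.35), true 0.90 | 93.4% | 96.1% |
| Positives ~ Binomial(80, 0.35), true 24/26 | 88.6% | 96.2% |

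At n = 28 and 0.90, the planned lower limit lies above the truth in 5.2% of trials (nominal 2.5%), all from 28/28.

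**5. The other measures at planning values.**

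- NPV: true negatives 52 × 0.76 = 39.52, false negatives 28 × 0.10 = 2.8, so NPV = 39.52/42.32 = 0.934. At n = 42, coverage is 94.2% (Wilson 94.4%), with lower-limit error 5.7%. At 42/42 the lower limit is 0.988, against 0.916 for Wilson. With the number of test-negative bundles varying, coverage is 93.9% (Wilson 96.2%), or 88.6% (Wilson 95.9%) if sensitivity is 24/26.
- Specificity (0.76, n = 52): 93.9%, against 95.1% for Wilson.
- PPV (25.2/37.68 = 0.669, n = 38): 95.5%, against 96.3% for Wilson.

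Specificity and PPV are little affected.

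**The case against.** The strongest reply is that, at exactly the planned inputs, changing the method gains almost nothing. Total coverage is 94.3% against 94.5%, and Wilson moves the error to the other side (5.5% in the upper limit, against 0.5% as planned). The striking 0.982 needs 28/28, a 5% event at 90% sensitivity. At 26/28 and 27/28 the planned limits still lie below 0.90, so they do not exclude the anticipated value; they are 4 to 5 points above Wilson's. The tail-area test is the criterion of an exact interval, which an asymptotic method does not promise, and Wilson also slightly exceeds 2.5%. The printed widths do reproduce once a proportion is bounded at 1. Finally, this is a single-arm pilot without a success threshold, and Section 10.6, writing of the PET–MRI comparison, calls its data hypothesis generating.

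Most of this is right and limits the weight of the point: the parity at 28 bundles and 90%, the rarity of 28/28 there, and the absence of a decision rule all stand. It does not remove the point. The number of positive bundles will not be fixed at 28, and with that variation the planned coverage falls below Wilson's even at 90%. The deficit is large at the protocol's own preliminary 24/26. Wilson's excess over 2.5% is small (2.7% to 3.1%), whereas the planned method's runs from 8.8% to 60.4%. Bounding at 1 explains the printed width but leaves the lower limit as it is.

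**Conclusion.** The point holds and should be fixed; its weight is minor to moderate. Followed as written, the plan would report a lower limit for sensitivity that is about 4 points (26/28) to 10 points (28/28) above Wilson's, over a range of results with 46% probability at the planned sensitivity. NPV behaves alike. The 0.23 in Section 10.3 is not an arithmetic error, but it rests on a truncation rule that the plan does not state. The harm is misstated precision, not a wrong trial decision.

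These figures assume the planned 80 bundles, 35% prevalence and independent bundles. Two bundles per patient is a separate matter, and inflating the standard error for it would not repair the planned method: at 28/28 the standard error is zero and the limit stays at 0.982.

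**What to change.** In Section 10.5, replace both interval sentences with: *Sensitivity, specificity, PPV and NPV will be summarized with two-sided 95% Wilson score intervals.*

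In Section 10.3, replace the last sentence with: *Widths are based on the Wilson score interval; with 28 positive and 52 negative bundles they are 0.230 for sensitivity (90%) and 0.227 for specificity (76%).* Present the widths as expected values, not maxima. The 90% case corresponds to 25.2 of 28; at the attainable 25/28 the Wilson width is 0.235, and the planned method also exceeds 0.23 there (0.240 cut, 0.265 uncut).

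Any adjustment for paired bundles can be applied to the Wilson interval through an effective number of bundles, with the Section 10.3 widths then recalculated. The documents give no design effect. Under assumed values of 1.0, 1.2 and 1.5, the Wilson lower limit at 28/28 is 0.879, 0.859 and 0.829.

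The cost is a change of wording, with no effect on design or data collection. The price is less favourable lower limits when few bundles are missed (0.815 becomes 0.774 at 26/28; 0.982 becomes 0.879 at 28/28), and no coverage gain at exactly 28 bundles and 90%. If the current method is kept, both sections should at least state that limits are cut at 0 and 1, which leaves the lower-limit problem in place.

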10.6 Analysis of Secondary Objectives

The frequency of proper treatment changes directed by PSMA-PET compared to MRI will be summarized along 95% CI for all evaluable subjects, and separated for 3 areas important for genito-urinary function including: 1) Bladder neck, 2) Nerve bundles, 3) Urethral Sphincter (Figure 4). We will use the McNemar test to compare the sensitivity and specificity values between PET and MRI although data from this pilot study is considered hypothesis generating only due to the small sample size.

The quality of life data including IIEF-15 (Erectile function score), EPIC-26 (Pad use), SF-36 (overall mental and physical health domains) are longitudinal data, which will be analyzed separately. The analysis will start with the graphical representation of the data, where

mean and the standard of mean at each time point will be plotted and linked over time. An exploratory statistical modelling approach will be conducted to analyze the change over time. In particular, a mixed effects model will be used to analyze the data.

The parametric kinetic modeling data will be assessed for goodness-of-fit of the measured regional tissue time-activity curves to the applied kinetic model. Additionally, the images derived by voxel-wise kinetic modeling will be visually compared to standard reconstructions of the integrated regional concentration of radioactivity, assessing apparent lesion size, lesion position, and lesion/background contrast.

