4.2 Secondary

1) Quantify the frequency of proper treatment changes directed by PSMA-PET

2) Compare PSMA-PET performance for predicting extra-prostatic extension to standard-of-care assessments.

Exploratory Endpoints:

3) Assess quality of life changes from preoperative baseline:

IEF-15 (Erectile function score),

EPIC-26 (Pad use),

SF-36 (Overall mental and physical health domains)

4) To assess whether kinetic modeling tools are useful for improving detection of the location and extent of tumor in ^{68}Ga -PSMA-11 PET/CT images. (Going beyond the standard PET map of regional radiotracer concentrations, to additionally examine differences in regional pharmacokinetics in order to possibly better differentiate benign and neoplastic tissue.)

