5.2 Secondary

1) Rate of treatment changes and rate of treatment changes that were appropriate based on pathology.

Exploratory Endpoints

- 2) Sensitivity/ Specificity/ PPV/ NPV for PSMA-PET vs. MRI vs. ultrasound-based nomogram.
- 3) IIEF-15 (Erectile function score), EPIC-26 (Pad use), SF-36 (overall mental and physical health domains).
- 4) Qualitative and quantitative evaluation of changes in PET image appearance after voxel-by-voxel application of kinetic modeling tools to define regional pharmacokinetics (compared to standard PET reconstructions showing simply the integrated concentration of regional radioactivity over the imaging period).

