8.2 Study Calendar

	Screening/ Baseline (-90 days)	Imaging (Day 1)	Surgery (Day 2- 45)	1 ⁶ month F/U	3 ⁶ Month F/U	6 ⁶ month F/U	1 ⁶ year F/U
REQUIRED ASSESSMENTS							
Informed Consent	X						
Inclusion/Exclusion	X						
Medical History ¹	X						
Quality of life Assessments ²	X			X	X	X	X
Surgeon plan (pre-PET)	X						
PSMA dose and PET scan		X					
SOC MRI ³		X					
Surgeon plan (post-PET) ⁴		X					
SOC prostatectomy			X				
Surgery plan (performed)			X				
Pathologic assessment of whole mount ⁵			X				

Footnotes:

1. Medical history may be obtained via medical records, as necessary.
2. Quality of Life Assessments include the following:
 - a. IIEF-15 Score (Erectile function)
 - b. EPIC-26 Questionnaire (Urinary function)
 - c. SF-36 Quality-of-life assessment
3. If the patient does not already have a recent SOC MRI (within 6 months), it will need to be completed as per SOC prior to the PSMA-PET scan.
4. This should be completed within 9 days of the scan.
5. The pathologic whole mount assessments may be batch completed per pathology discretion
6. 1-month follow-up is 4-6 weeks. 3-month follow-up is +/-1-month, 6-month and 12-month follow-up are +/-2-months

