Alternatively, we will also assess characterization of the input function will be generated by placing a 3D volume of interest over the abdominal aorta (possibly including the bifurcation) to capture the needed measures of blood pool radioactivity.

- The PET read will be done by a board-certified nuclear medicine specialist (e.g. [name] or similar) and the MRI read will be done by a board certified MR radiologist (e.g. [name] or similar). Suspicious lesions will be marked in a blinded fashion.
- AE assessment: AEs will be assessed at the time of ⁶⁸Ga-PSMA-11 administration any event **not expected** is collected including but not limited to: rash and shortness of breath.
- Safety monitoring following radiopharmaceutical administration will consist of visual and verbal monitoring of the patient after injection, and during and at the conclusion of the PET/CT procedure, with any apparent patient abnormalities, reactions or reported effects noted in the study records.
- The nuclear medicine technologists administering the radiopharmaceutical are responsible for immediately reporting any adverse or unexpected events to the principal investigator or clinical designee, who will report the occurrence of any adverse events to the IRB.
- As in most clinical nuclear medicine procedures, these radiopharmaceuticals are administered at a sub-pharmacologic doses. Adverse events are exceedingly unlikely, as ⁶⁸Ga-HBED-CC has been clinically employed, extensively and without reported incident, in clinical patient diagnostic imaging studies in prostate cancer patients in Germany and other European countries, as well as in over 400 patients locally.

- If there is a discrepancy between the PSMA and conventional MRI scan, the investigators will discuss the treatment plan with the patient at the investigator's discretion. This will be completed through a pre-surgery clinic or virtual visit within 9days of the PET/CT scan.

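### Section 10.6 counts treatment changes against MRI, but the endpoint is a change of surgical plan and no MRI-based plan is recorded; the reference plan and its timing need defining

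*Combined protocol and SAP*

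**What the plan says.** The objective in Section 4.2 is to "Quantify the frequency of proper treatment changes directed by PSMA-PET". The matching endpoint in Section 5.2 is "Rate of treatment changes and rate of treatment changes that were appropriate based on pathology". Neither names MRI or any other reference.

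The Study Calendar (8.2) has three rows for the surgical decision:
- "Surgeon plan (pre-PET" in the Screening/Baseline column (up to 90 days before imaging)
- "Surgeon plan (post-PET" in the Imaging column, due within 9 days of the scan (footnote 4)
- "Surgery plan (performed" in the Surgery column

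There is no row for a plan based on MRI.

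The only analysis rule for the endpoint is in Section 10.6: "The frequency of proper treatment changes directed by PSMA-PET compared to MRI will be summarized along 95% CI for all evaluable subjects", with a further split into bladder neck, nerve bundles and urethral sphincter. No sentence ties this count to the recorded plans, and none says how a plan implied by MRI would be derived.

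On timing, inclusion criterion 3 (6.1) admits patients whose MRI is only scheduled. For patients without a recent MRI, footnote 3 of the calendar says "it will need to be completed as per SOC prior to the PSMA-PET scan". It does not require the MRI to come before the baseline plan.

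**The concern.** An MRI read is not a surgical plan. Section 3.1 says that surgery is currently guided by MRI together with ultrasound biopsies, and that wide resection is often planned on suspicion from biopsy and imaging. The surgeon's pre-PET intention can therefore differ from what MRI alone would imply. An analyst who follows 10.6 to the letter would compare PET with MRI and obtain a measure of how often the scans disagree, not of how often surgery was altered.

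This is the only endpoint that Section 5.2 lists above its exploratory heading, and it is the one that speaks to the trial's title question of surgery guidance. As written, two analysts could report different rates from the same data.

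**Working it through.** **Is there a stated figure to reproduce?** Not for this endpoint. Section 10.3 gives precision only for sensitivity and specificity. The issue here is one of definition, so the check is to set the two possible counts side by side.

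**Step 1: where the counts differ.** Take one nerve bundle. The literal count scores a proper change when PET and MRI disagree and pathology supports PET. The plan-based count scores one when the post-PET plan differs from the pre-PET plan and pathology supports the post-PET plan.

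| Case | Pre-PET plan | MRI | PET | Post-PET plan | Pathology | Literal count | Plan-based count |
|---|---|---|---|---|---|---|---|
| A | resect | negative | positive | resect | extension | change | no change |
| B | resect (biopsy-driven) | negative | negative | spare | no extension | no change | change |
| C | spare | negative | positive | resect | extension | change | change |
| D | spare, recorded before MRI | positive | positive | resect | extension | no change | change, though MRI alone may have prompted it |

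A and B are the two errors of the literal count. D is an error of a plan-based count whose first plan predates the MRI.

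**Step 2: net error of the literal count.** Assume the pre-PET plan already includes MRI, so that D does not arise. Let *a* be the bundles where the scans disagree in PET's favour but the plan did not change, *b* those where the scans agree but the plan properly changed, and *c* those where both happened.

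- Literal count = c + a
- Plan-based count = c + b
- Error = a − b

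The documents give none of *a*, *b* or *c*. The preliminary data in Section 3.1 report that PET would have changed the plan in 18/33 cases, including sparing 12 nerve bundles and avoiding sparing in 4 cases. Switches to sparing are thus not rare, but MRI status is not given for these cases, so they cannot be assigned to *b* or *c*.

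**Step 3: an illustration, to show what drives the answer.**

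From Section 10.3: 80 evaluable bundles, prevalence 35%, PET sensitivity 90%. Bundles with extension: 80 × 0.35 = 28. Bundles without: 80 × 0.65 = 52.

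Assumptions, not in the documents: MRI finds 50% of extensions, independently of PET, and resection was already planned in a share *s* of the bundles that MRI missed and PET found.

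- Missed by MRI, found by PET: 28 × 0.5 × 0.9 = 12.6
- s = 25%: a = 3.15, c = 9.45, and with b = 0 the ratio is 12.6/9.45 = 1.33
- s = 50%: a = 6.3, c = 6.3, and with b = 0 the ratio is 12.6/6.3 = 2.0

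The ratio is simply 1/(1 − s), the reciprocal of an assumed quantity, and it holds only if b = 0. A proper switch to sparing must fall among the 52 bundles without extension. The error cancels when b = a, that is at 3.15/52 = 6% of them for s = 25%, or 6.3/52 = 12% for s = 50%. Above those shares the literal count is too low. Modest case B frequencies therefore reverse the sign.

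**Step 4: timing.** The pre-PET plan belongs to baseline; MRI need only precede PET. For a patient whose MRI was pending at entry, the order baseline plan, MRI, PET, post-PET plan is allowed, and case D follows. The documents do not say how many patients this would be.

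**The case against.** The strongest reply is that naming MRI is loose wording for the MRI-informed standard-of-care plan. The sentence in 10.6 still counts treatment changes directed by PET, so a bundle whose plan did not change is not a change on its face. The synopsis sets PET against standard-of-care MRI, Section 8.1 describes the MRI as already done, and a pre-to-post comparison is the obvious use of the calendar's plan rows. On that reading cases A and B do not arise. This stands to the extent that the harm depends on how 10.6 is read. It does not remove the gap: no text adopts that reading, and 6.1 and footnote 3 allow a pre-PET plan made without MRI.

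A second reply is that removing MRI from the sentence deletes the only wording that separates PET's contribution from MRI's. That is correct for a bare pre-to-post comparison, and it is why a timing rule is needed.

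Two stronger readings are tempting. A reader might infer that the plan inflates PET's effect on management, by 1.3 to 2 times or otherwise. The documents do not support this: the multiplier restates an assumed overlap, covers only bundles with extension, and ignores case B. A reader might also take Section 8.3.2 ("If there is a discrepancy between the PSMA and conventional MRI scan, the investigators will discuss the treatment plan with the patient") as proof that changes will be counted from scan disagreement. That passage describes a conversation with the patient at the investigator's discretion; it is not a counting rule.

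**Conclusion.** The concern holds as a defect of definition. Section 10.6 names a comparator that the trial does not record as a plan, while the plans that would answer the endpoint are recorded but not used in any analysis rule. Read literally, the count can err in either direction. Its size and net sign cannot be derived from the documents; the figures in the illustration rest on an assumed MRI sensitivity, independence of the scans and an assumed overlap. Separately, the calendar does not ensure that the pre-PET plan includes the MRI, so a plan-based count also needs a timing rule.

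The impact is limited. The endpoint is secondary and descriptive, no test or decision rule depends on it, and the primary sensitivity and specificity are unaffected. It is still worth settling before analysis, because the reported rate depends on the reading chosen.

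**What to change.** - **Section 10.6:** replace the reference to MRI with a definition. A treatment change is a difference between the pre-PET and the post-PET surgeon plan at the same structure (bladder neck, each nerve bundle, urethral sphincter). It is proper if pathology at that structure supports the post-PET plan.
- **Section 8.2:** add a footnote that the pre-PET plan is recorded, or updated, after the MRI has been read and before PET results are disclosed to the surgeon.
- **PET-MRI disagreement:** report it only under the accuracy comparison.

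The cost is one sentence and one footnote. Both plans are already collected. The downside is that, for patients whose MRI was pending at baseline, the pre-PET plan form has to be completed or updated after the MRI.

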5 CRITERIA FOR EVALUATION

5.1 Primary

1) Sensitivity and Specificity of PSMA-PET imaging for detecting extra-prostatic extension of cancer at the nerve bundles

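### The exploratory PET-versus-MRI accuracy comparison rests on a McNemar test alone: no interval for the paired difference, no allowance for two bundles per man, and no method for comparing PPV, NPV or the nomogram

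*Combined protocol and SAP*

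**What the plan says.** Section 4.2 lists, under Secondary, the objective "Compare PSMA-PET performance for predicting extra-prostatic extension to standard-of-care assessments". The matching endpoint stands under the exploratory heading of section 5.2: "Sensitivity/ Specificity/ PPV/ NPV for PSMA-PET vs. MRI vs. ultrasound-based nomogram". The synopsis also puts it in the exploratory row.

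For accuracy, section 10.6 gives one sentence: "We will use the McNemar test to compare the sensitivity and specificity values between PET and MRI". It continues that "data from this pilot study is considered hypothesis generating only due to the small sample size". It does not state the unit of the test, but section 10.3 computes sensitivity and specificity over left and right bundles, so bundles are the natural reading.

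Two other places come close:

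- Section 10.5 states that "PPV and NPV will also be summarized along with 95% CI using the simple asymptotic method with continuity correction". This falls under the primary objective, whose criterion in section 5.1 is "Sensitivity and Specificity of PSMA-PET imaging for detecting extra-prostatic extension of cancer at the nerve bundles".
- Section 10.6 also has "The frequency of proper treatment changes directed by PSMA-PET compared to MRI will be summarized along 95% CI for all evaluable subjects". That is an interval for treatment changes, which is a different endpoint.

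**The concern.** A study that disclaims confirmatory inference is most useful when it reports how far apart two tests are and how uncertain that distance is. A McNemar p-value gives neither. With few discordant bundles, a non-significant result is compatible with a sizeable gain or loss.

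McNemar compares two calls on the same set of units. That suits sensitivity (all bundles with extension) and specificity (all bundles without). It does not suit PPV or NPV, because PET-negative and MRI-negative bundles are different, partly overlapping sets. NPV bears directly on what the trial studies, namely whether a bundle called clear by imaging is in fact clear.

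The ordinary McNemar test and the usual paired intervals also treat the two bundles of one man as independent, and nothing in section 10.6 corrects for that.

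**Working it through.** **Inputs from section 10.3.** 50 men give 100 bundles. With about 20% not evaluable, "Then we could have at least 80 data points". Prevalence of extra-prostatic extension is 35%, so 0.35 × 80 = 28 bundles with extension and 52 without. Anticipated PET sensitivity is 90% and specificity 76%.

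**The plan's own figures.** The interval is p ± [1.96·√(p(1−p)/n) + 1/(2n)], cut at 1.
- Sensitivity: 0.90 ± (0.111 + 0.018), or 0.771 to 1.000. Width 0.229 (stated: at most 0.23).
- Specificity: 0.76 ± (0.116 + 0.010), or 0.634 to 0.886. Width 0.251 (stated: at most 0.25).

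Both reproduce to rounding. They describe PET alone; the documents give no precision for the PET–MRI difference.

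**Assumptions.** The documents give no MRI sensitivity or specificity for extra-prostatic extension and no PET–MRI discordance. Those values are assumed below, and bundles are treated singly unless stated.

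**What the p-value leaves out.** Let b be bundles called correctly by PET only, c by MRI only, and n the bundles in the stratum. The difference is (b − c)/n. The exact p is 2·P(X ≤ min(b, c)) with X binomial(b + c, ½), so n does not enter it.
- b = 3, c = 8, n = 52: p = 2 × (1 + 11 + 55 + 165)/2048 = 0.23. The difference is −5/52 = −10 points, with a 95% score interval for paired proportions of −23 to +3. Not significant, yet a 23-point loss of specificity is not excluded.
- n = 28: splits of 6 vs 0 and 14 vs 4 both give p = 0.031. The differences are 6/28 = 21 points and 10/28 = 36 points.

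**Power if the test stands alone.** With MRI sensitivity assumed at 70% against PET's 90% and n = 28, exact McNemar power is about 33% if the tests are independent given pathology, and about 50% at the least possible discordance.

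**Predictive values.** NPV = TN/(TN + FN), with TN = specificity × 52 and FN = (1 − sensitivity) × 28.

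| Test | Sens / spec | NPV | Gap to PET |
|---|---|---|---|
| PET (plan) | 90 / 76 | 39.52/42.32 = 93.4% | – |
| MRI (assumed) | 50 / 76 | 39.52/53.52 = 73.8% | 19.5 points |
| MRI (assumed) | 50 / 85 | 44.2/58.2 = 75.9% | 17.4 points |
| MRI (assumed) | 70 / 76 | 39.52/47.92 = 82.5% | 10.9 points |
| MRI (assumed) | 70 / 85 | 44.2/52.6 = 84.0% | 9.4 points |

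The denominators differ: about 42 PET-negative bundles against 48 to 58 MRI-negative. This is why McNemar does not apply.

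**Precision to expect from an interval.** The expected width is 2 × 1.96·√{[p10 + p01 − (p10 − p01)²]/n}, where p10 and p01 are the two discordance probabilities.
- Sensitivity difference, MRI at 70%: 0.41 under independence (p10 = 0.27, p01 = 0.07), and 0.30 at least discordance.
- Sensitivity difference, MRI at 50% to 80%: 0.43 down to 0.37 under independence.
- Specificity difference, MRI at 60% to 90%: 0.28 to 0.35 under independence.
- An assumed design effect of 1.5 for two bundles per man widens 0.41 to 0.50.

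**The case against.** McNemar is a standard test for paired sensitivity and specificity. No success criterion or decision depends on it, the sample size rests on PET precision alone, and the plan limits the comparison to generating hypotheses. All of this stands and keeps the weight low.

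A reader might infer that the plan will show no size of difference at all. The documents do not support that. The endpoint requires the values for each modality, so the point difference follows by subtraction, and nothing restricts reporting to p-values. What is missing is the interval.

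A reader might also infer that PPV and NPV will go unreported for MRI. That goes too far: the endpoint can be read as four measures set side by side, and section 10.5's interval method could be extended to MRI. But that section serves the PET-only primary objective, so the extension is an inference. Two separate intervals would still not give an interval for a paired difference, which depends on the discordant counts.

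Finally, the NPV gap rests on assumed MRI accuracy and is an illustration, not a forecast.

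**Conclusion.** The gap is real but minor. For the exploratory accuracy endpoint, section 10.6 specifies a test of two of the four named measures for one of the two comparators. It gives no interval for the paired difference, no allowance for two bundles per man, no comparative method for PPV or NPV, and none for the nomogram.

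The illustrations show that a non-significant p of 0.23 can sit with an interval reaching a 23-point loss, and that an NPV gap of about 9–20 points would have no planned comparison. They rest on assumed discordance and assumed MRI accuracy. The interval also rests on independent bundles, and the documents give no within-man correlation.

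The McNemar test is not the wrong test for paired sensitivity and specificity, and the primary analysis is untouched. The finding is that the comparative analysis is incomplete.

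**What to change.** In section 10.6, make the main PET–MRI result the PET-minus-MRI paired difference in sensitivity, specificity, PPV and NPV. Give each a 95% interval from a bootstrap that resamples men and keeps both bundles of a man together. A GEE clustered on patient is an alternative; for PPV and NPV it would regress extension status on test type among positive and among negative calls. Apply the same analysis to PET against the nomogram. Keep McNemar as a supplement and state which version (exact or asymptotic) is used. Do not use a paired score interval that treats bundles as independent; it appears above only to illustrate scale.

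The cost is a paragraph of plan wording and a little more code, with no new data. The downside is that the intervals will be wide (about 0.4 to 0.5 for sensitivity under the independence and design-effect assumptions above). That is what the data can support, and the report should show it.
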